### **3. SUBJECT DISPOSITION**

#### **3.1. Subject Enrollment and Disposition**

For Part 1 a summary of subject enrollment will present counts and percentages of subjects who were screened, enrolled, randomized and were treated with at least one dose of study drug post-randomization, completed double-blind phase and discontinued during the double-blind phase.

For Part 2 a summary of enrollment will present counts and percentages of subjects who entered OLE, were treated in OLE, completed OLE and discontinued during OLE..

A summary of subject disposition will be provided by treatment group and period for each study part. This summary will present the number of subjects who were dispensed, treated, discontinued treatment and the reasons for early discontinuation. The summary will be based on the safety analysis set for Part 1 and all subjects who entered Part 2 for Part 2.

#### **3.2. Extent of Study Drug Exposure and Adherence**

##### **3.2.1. Duration of Exposure to Study Drug**

Exposure to study drug in Part 1 will be summarized by frequencies and percentages based on the safety analysis set using the following categories:

- run-in
- double-blind
  - ZNS only
  - Placebo only
  - Both

In Part 2 subjects will be summarized by number of doses taken:

- < 4 doses
- 4 to < 8 doses
- 8 to < 12 doses
- 12 to < 24 doses
- 24 to < 36 doses
- $\geq$  36 doses

Note that during the open-label period subjects are allowed to take a second dose of study drug within 72 hours of the start of this migraine headache. This dose counts towards the total count of study drug dose.

### **3.3. Protocol Deviations**

Protocol deviations, such as subjects who did not meet eligibility criteria at study entry and those occurring after subjects entered the study, are documented during routine monitoring and are reviewed by the medical monitor. Details of protocol deviations for each study site will be provided by the Clinical Operations Group to the Statistics and Data Management Group prior to database finalization. All protocol deviations will be listed for both study parts.

## **4. BASELINE CHARACTERISTICS**

### **4.1. Demographics**

Subject demographic variables (age, sex, race, and ethnicity) will be summarized for Part 1 for the safety analysis and for Part 2 for the OLE analysis set using descriptive statistics. Age will be calculated at the appropriate study part baseline. Age will also be dichotomized into 6 to < 9 and 9 to 11 years. Proportion of female subjects who are postmenarcheal will also be provided.

A by-subject demographic listing will be provided by subject ID number in ascending order for each study part.

### **4.2. Other Baseline Characteristics**

Other baseline characteristics include body weight (in kg), height (in cm), and body mass index (BMI; in kg/m^2) at baseline of each study part. Weight in pounds (lbs) will be converted to kg using the conversion factor 1 lb = 0.45359 kg. Height in inches will be converted to centimeters using the conversion factor 1 in = 2.54 cm. These baseline characteristics will be summarized for the safety analysis set for Part 1 and for the OLE analysis set for Part 2 using descriptive statistics. Weight will be dichotomized into < 50 kg and ≥ 50 kg.

A by-subject listing of other baseline characteristics will be provided by subject ID number in ascending order, along with the demographic information.

### **4.3. Migraine Headache Disease Characteristics and Measures**

The age at onset of migraine attacks, average number of migraine headaches per month, average number of migraine headache days per month, and average number of non-migraine headache days/month will be summarized using descriptive statistics for Part 1 for the safety analysis set and for Part 2 for the OLE analysis set.

The following categorical variables will be summarized using the safety analysis set by frequencies and percentages: type of migraine (with aura, without aura, both), duration of typical untreated moderate/severe migraine (< 3 hours, ≥ 3 to 4 hours, > 4 to 6 hours, > 6 to 8 hours, > 8 hours), nausea (yes/no), light sensitivity (yes/no), sound sensitivity (yes/no), and vomiting (yes/no) with a typical migraine.

### **4.4. Medical History and Physical Findings**

Summaries of clinically significant medical history and abnormal physical findings at screening will be provided for Part 1 for the safety analysis set and for Part 2 for the OLE analysis set.

## **5. EFFICACY ANALYSES**

### **5.1. Primary Efficacy Endpoint in Part 1**

A patient diary is used to collect the patients' self-assessment of headache pain intensity. Pain intensity is rated on a 4-point scale: severe (3), moderate (2), mild (1), and none (0).

The primary efficacy endpoint is the proportion of subjects with pain-free status at the 2-hour time point for the high dose group during the double-blind phase of the study. Pain-free status is defined as a reduction in the headache pain intensity rating from moderate (2) or severe (3) pain at predose to none (0) at 2-hour post dose, without using rescue medication and without napping/sleeping prior to the 2-hour assessment.

For the primary efficacy endpoint analysis, all high-dose subjects in the FAS are included.

The primary endpoint will be analyzed using a generalized estimating equation (GEE). The model includes treatment, period, sequence, weight group (at randomization), and predose (immediately prior to study drug administration) headache pain intensity. The logit link function is used with an unstructured within subject covariance matrix. Odds ratio, p-value for the treatment effect and the corresponding 95% confidence interval will be presented.

### **5.2. Sensitivity and Supportive Analyses of the Primary Efficacy Endpoint**

#### **5.2.1.1. Carryover Effect**

The presence of a carryover effect will be estimated by the sequence effect. If the sequence effect is found to be significant at a 0.05 level, the following analyses will be conducted using data from Period 1 as corroborative evidence:

- Cochran-Mantel-Haenszel (CMH) test stratified by center.  
Although this comparison will be underpowered, consistent trend with the analysis from the primary analysis will be considered as corroborative evidence. In addition to the CMH test, the treatment difference, and 95% confidence interval, will be estimated for Period 1 via a logistic model with treatment, weight group, and predose severity score as factors.
- The percentage of patients achieving pain-free status by sequence and period will be summarized. This analysis will provide information on whether there is a differential dropout rate after each treatment and whether treatment by period interaction is evident.

In addition, McNemar's test for each sequence to compare ZNS with placebo will also be performed.

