## 1.2. Sample Size and Power

Part I of this study is a randomized, double-blind, placebo-controlled, 2-period, crossover outpatient study with a 6-week placebo run-in period.

Approximately 426 subjects will be enrolled to the placebo run-in period to randomize 288. With the 5:1 (high dose:low dose) randomization ratio for each of the two weight strata, it is estimated that 240 subjects will be randomized in the high-dose group and 48 subjects will be randomized to the lower dose level.

The sample size is based on detecting a difference in the percentage of subjects treated with a high dose (2.5 mg in the <50 kg weight stratum and 5 mg in the ≥50 kg weight stratum) who are pain free at 2 hours between ZNS and placebo. In this crossover trial, 240 high-dose-treated subjects will be adequate to detect a clinically relevant difference of 0.11 in the percentage of subjects who are pain free at 2 hours between ZNS and placebo as statistically significant (0.05, two tailed) with 90% power assuming a standard deviation of 0.5.

Approximately 48 subjects will be randomized in the low dose level (1 mg in the <50 kg weight stratum and 2.5 mg in the ≥50 kg weight stratum). The data from the low dose level will be summarized to explore dose-response relationship.

Based on other migraine crossover studies, dropout rates during the placebo run-in period ranged from 12% to 50%. Based on this, approximately 426 subjects will be enrolled into the placebo run-in period to randomize 288. This allows for approximately 32% dropout during placebo run-in period.

Approximately 100 subjects who complete the double-blind crossover phase will enter the 6-month OLE to enable at least 50 subjects to complete at least 6 months treating on average at least one migraine attack per month (treating up to 4 migraine attacks per month) with ZNS. Part II of the study is an OLE with subjects who successfully complete Part I of the study.

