## **2. GENERAL CONSIDERATIONS FOR DATA ANALYSIS**

Part 1 and 2 of the study will be analyzed separately. Separate sets of tables, listings and figures will be prepared for Part 1 and Part 2.

After all subjects have completed the double-blind phase of the study (Part I) or prematurely discontinued from the study, all data in Part I will be cleaned, the database will be frozen (soft lock), the study will be unblinded, and an analysis of Part I (double-blind) data will be performed. This will be the primary analysis of the study and a type I error rate (5%) will be allocated for this analysis.

All statistical tests will be 2-sided and performed at the 5% significance level, without multiplicity adjustment.

Likewise, after all subjects have completed Part II (OLE) of the study or prematurely discontinued from the study, all outstanding data queries have been resolved or adjudicated as unresolvable, and the data have been cleaned and finalized, the final analysis of the data will be performed. This final analysis will mainly focus on the OLE.

Analysis results will be presented using descriptive statistics. For categorical variables, the number and percentage of subjects in each category will be presented; for continuous variables, descriptive statistics (the number of subjects [n], mean, standard deviation [SD], median, minimum, and maximum) will be presented.

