### **2.3. Randomization**

Subjects are randomly assigned to one of the two treatment sequences, stratified by weight and dose group, via the interactive web response system (IWRS). In each dose group, the assignment to the two treatment sequences (ZNS:placebo or placebo:ZNS) is in a 1:1 ratio. The randomizations scheme is as follows.

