### **5.5. Changes From Protocol-Specified Efficacy Analyses**

If a subject naps or sleeps within 2 hours after dosing with study drug for a particular treatment period, the subject will be considered a non-responder for all diary time points up to and including the 2-hour diary time point for that treatment period.

The randomized population is replaced by the full analysis set. The completers population is further clarified as the double-blind completers analysis set.

The protocol inadvertently states that the McNemar's test was to be performed for Period 1 data. This SAP has corrected that the McNemar's test will be performed for each sequence.

Additional endpoints were added to the OLE endpoints to further elucidate the effect of ZNS:

- Proportion of subjects experiencing 2-hour pain free for  $\geq 20\%$ , 40%, 60%, and 80% of their treated moderate to severe migraine headaches.
- Proportion of treated moderate to severe migraine headaches that reduce to pain free at 2 hours:
  - o Descriptive summaries (mean, SD, median, min, max)
  - o Categorical summaries of  $\geq 20\%$ , 40%, 60%, and 80% of treated headaches

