## 8.4. Sensitivity Analysis McNemar Test

```
proc freq data=...;
  by trtseqp;
  tables avalc1*avalc2 / agree;
run;
```

The input dataset needs to include a record per subject with variables:

- AVALC1: responses in treatment period 1
- AVALC2: responses in treatment period 2
- TRTSEQP: planned sequence of treatments (ZNS-Placebo or Placebo-ZNS)

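### McNemar's test within each sequence cannot separate treatment from period, and the Period 1 supportive results appear only after a significant sequence test that shares their data

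*SAP*

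**What the plan says.** Section 5.2.1.1 estimates carryover by the sequence effect and makes the further work conditional on it: "If the sequence effect is found to be significant at a 0.05 level, the following analyses will be conducted using data from Period 1". Listed under that condition are a centre-stratified CMH test, a logistic model for the Period 1 treatment difference, and a table of pain-free percentages by sequence and period. The section concedes that the Period 1 comparison lacks power, and counts a trend in line with the primary result as corroboration.

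It then adds that the McNemar "test for each sequence to compare ZNS with placebo will also be performed". Section 8.4 codes this by sequence as "tables avalc1*avalc2 / agree", that is, Period 1 response against Period 2 response. Section 5.5 presents it as a correction of the protocol, which had placed McNemar's test on Period 1 data: the "test will be performed for each sequence".

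Section 2 adds: "All statistical tests will be 2-sided and performed at the 5% significance level, without multiplicity adjustment". The primary GEE in section 5.1 includes both period and sequence.

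**The concern.** In Sequence 1 every ZNS response comes from Period 1 and every placebo response from Period 2. In Sequence 2 it is the reverse. Inside one sequence the treatment contrast and the period contrast are therefore the same contrast, and McNemar's test cannot tell them apart. The primary model allows for a period effect and this analysis drops that allowance. No rule says how the two McNemar results are to be read together.

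The second issue is the condition on the Period 1 analyses. A Period 1 comparison of randomised groups is valid by itself. The sequence test, however, uses each child's Period 1 response as well as the Period 2 response, so selecting on its significance also selects on the Period 1 difference. The sequence-by-period table, which would show a period effect and help a reader interpret McNemar, sits behind the same condition.

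At stake is whether these supportive results can be read as support. The primary result is not at stake.

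**Working it through.** **Inputs from the SAP.** Two-sided 5% level (section 2). From section 1.2: "240 high-dose-treated subjects will be adequate to detect a clinically relevant difference of 0.11", "with 90% power assuming a standard deviation of 0.5". From section 2.3: "the assignment to the two treatment sequences (ZNS:placebo or placebo:ZNS) is in a 1:1 ratio", so about 240/2 = 120 high-dose children per sequence. Pain-free rates, period effect and within-child correlation are not given and are assumed below.

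**The plan's own figure.** Reading 0.5 as the SD of the within-child difference, n = (0.5 × (1.960 + 1.282)/0.11)² = 217.1, so 218. With 240 the power is 92.6%. The stated number is conservative and does not affect this point.

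**McNemar under a period effect alone.** Assume no treatment effect, latent (bivariate normal) correlation 0.5, and 120 children per sequence with both periods observed.

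- *20% in Period 1, 25% in Period 2.* The probability of being pain-free in both periods is 0.102. Discordant probabilities are 0.20 − 0.102 = 0.098 (Period 1 only) and 0.25 − 0.102 = 0.148 (Period 2 only), or 11.8 and 17.8 expected children. The expected statistic is (17.8 − 11.8)/√29.5 = 1.10. Simulated rejection is about 20% per test.
- *20% and 30%.* The joint probability is 0.115. Expected discordant counts are 10.2 and 22.2, and the statistic is 12.0/√32.3 = 2.11. Simulated rejection is about 57% per test.

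With the higher rate in Period 2, Sequence 1 leans to placebo and Sequence 2 to ZNS.

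Over a wider grid (rate 0.15 or 0.25, latent correlation 0.3 or 0.6), each test rejects about 5% with no period effect, 16% to 25% with a period effect of 0.05, 45% to 70% with 0.10, and 78% to 95% with 0.15. With a true effect of 0.11 and a period effect of 0.10, one sequence detects ZNS in about 4% of trials and the other in about 99%.

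**Mainland-Gart on the same data.** This test crosses sequence with the period in which the discordant child was pain-free. A period effect alone gives the same expected split in both rows (11.8 : 17.8 in each), so the odds ratio is 1. Simulated rejection is 4.8% to 5.4% for every assumed period effect from 0 to 0.15.

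**The condition on Period 1.** As a stand-in for the GEE sequence term, compare the sequences on each child's total Y1 + Y2. With common variance and within-child correlation ρ, the correlation between this statistic and the Period 1 statistic is (1 + ρ)/√(2(1 + ρ)) = √((1 + ρ)/2).

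With no treatment effect and no carryover, the sequence test is significant in 5% of trials. Among those:

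| ρ | correlation of the two statistics | Period 1 test rejects |
|---|---|---|
| 0 | 0.707 | 34% |
| 0.3 | 0.806 | 45% |
| 0.5 | 0.866 | 53% |

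Simulation of binary responses gives 33% to 50%. As a share of all trials the table's figures are 0.05 × 0.34 = 1.7% to 0.05 × 0.53 = 2.7%, half of them against ZNS. Run unconditionally, the Period 1 test rejects 4.7% to 5.2%.

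With carryover strong enough to open the condition in 50% to 90% of trials, the conditional two-sided Period 1 error is about 3% to 5%. The estimate still moves. At 50% opening the sequence statistic is centred at 1.96, its mean excess given significance is √(2/π) = 0.80, and the Period 1 statistic shifts by 0.707 × 0.80 = 0.56 to 0.866 × 0.80 = 0.69 standard errors. At an assumed 20% rate the standard error is √(2 × 0.2 × 0.8/120) = 0.052, so the shift is about 3 to 4 percentage points.

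With a true difference of 0.11 and no carryover, the mean Period 1 difference among trials that open the condition is about 0.20 to 0.23, or about 0.00 to 0.02, depending on the direction of the sequence effect.

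**The case against.** A reader might infer that neither analysis can corroborate anything. The SAP does not support that. Both sequences are reported, and a period effect pushes them in opposite directions. Two McNemar results that both favour ZNS could not be put down to period: that joint false-positive rate is 0.1% or less in the simulations. The Period 1 comparison is sound when run regardless of the sequence test.

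A reader might also quote the chance that at least one McNemar test rejects (36% and 82% in the two scenarios) as a false-positive rate for the trial. The SAP has no rule that one significant McNemar test counts as success. The 10-point period shift is also an assumption, almost as large as the 11-point effect the trial is powered for.

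Nor is 34% to 53% a general error rate. It belongs to chance openings without carryover. In the situation the condition was written for, real carryover, the test error is not inflated. The SAP never lets Period 1 replace the primary GEE and admits that the comparison is underpowered, so trial-level type I error is unaffected.

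The primary GEE already pools both sequences with period adjustment, so Mainland-Gart partly duplicates it, and calling the McNemar results descriptive would remove much of the harm. That is fair. What stands is that each McNemar test is described as a ZNS versus placebo comparison, which it is not, and that the condition can exaggerate or erase the Period 1 difference when it is shown.

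**Conclusion.** The point holds for two supportive analyses as specified. Each per-sequence McNemar test measures treatment plus period. This follows from the design and the code in section 8.4 and needs no assumption. Its size does: about 20% or 57% false rejection per test for assumed pain-free rates of 20% then 25% or 30%, latent correlation 0.5, and 120 children per sequence.

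The 0.05 condition raises the Period 1 error to 34% to 53% in the 5% of trials where it opens by chance. With real carryover the error is near or below 5%, with some bias left in the estimate. These figures use unadjusted statistics in place of the GEE sequence term, the centre-stratified CMH test and the adjusted logistic model.

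The SAP leaves unclear whether the McNemar tests are also subject to the condition. The confounding is the same either way. The primary estimate and its 5% error rate are unaffected. The change is worth making, but the primary conclusion does not depend on it.

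**What to change.** 1. In sections 5.2.1.1, 5.5 and 8.4, replace the two per-sequence McNemar tests with one Mainland-Gart test (or Prescott's test), which compares the direction of discordant pairs between the two sequences.
2. In section 5.2.1.1, remove the 0.05 trigger. Always report the Period 1 CMH and logistic results and the sequence-by-period table, labelled supportive. The Period 1 code in sections 8.2 and 8.3 can stay.

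The cost is SAP wording and one 2×2 PROC FREQ on discordant pairs. No new data are needed. The Period 1 comparison stays weak: with 120 per arm and SD 0.5, 0.11/(0.5 × √(2/120)) = 1.70, which is 40% power for 0.11. It should be read for its estimate and interval, not its p-value.

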#### **5.2.1.2. Completers Analysis**

An analysis on the completers analysis set will also be performed as corroborative evidence.

### 5.2.1.3. Multiple Imputation Analysis

If the dropout rate is > 20%, a multiple imputation analysis will be performed. The analysis will be as follows:

- a. Use logistic regression on Period 1 data to regress the response variable (0/1) on randomization weight group and treatment group.

$$\text{logit}(p) = \beta_0 + \beta_1 \text{trtp} + \beta_2 \text{wtgrp}$$

where  $p_j = \Pr(R_j = 1 | \text{trtp}, \text{wtgrp})$  and  $R_j$  is the response of subject  $j$ .

- b. For each observation with missing data in Period 2,
  - i. Calculate the predictive probability of response  $R_j = 1$   
$$p_j = \frac{\exp(\mu_j)}{1 + \exp(\mu_j)}, \text{ where } \mu_j = \hat{\beta}_0 + \hat{\beta}_1 \text{trtp} + \hat{\beta}_2 \text{wtgrp}.$$
  - ii. Draw a random uniform variable,  $u$ , between 0 and 1. If the value of  $u < p_j$ , impute  $R_j = 1$ ; otherwise, impute  $R_j = 0$ .
  - iii. Draw a random uniform variable,  $v$ , between 0 and 1. If  $v < 0.5$ , then impute baseline severity = 3; otherwise, impute baseline severity = 2.
- c. Analyze the data using the model as in primary analysis.
- d. Repeat the steps b-c above 25 times.
- e. Combine the results using Rubin's rule ([Rubin 1987](#)).

### 5.2.1.4. Tipping Point Analysis

In addition to the multiple imputation analysis, a tipping point analysis will be performed when the dropout rate is > 20%. The analysis will be carried out as follows:

- a. Use logistic regression on Period 1 data to regress response (0/1) on randomization weight and treatment group.

$$\text{logit}(p) = \beta_0 + \beta_1 \text{trtp} + \beta_2 \text{wtgrp}$$

where  $p_j = \Pr(R_j = 1 | \text{trtp}, \text{wtgrp})$ .

- b. For each observation with missing data in Period 2,
  - i. Calculate the predictive probability of  $R_j = 1$   
$$p_j = \frac{\exp(\mu_j)}{1 + \exp(\mu_j)}, \text{ where } \mu_j = \hat{\beta}_0 + \hat{\beta}_1 \text{trtp} + \hat{\beta}_2 \text{wtgrp}.$$
  - ii. Draw a random uniform variable,  $u$ , between 0 and 1.
    - If the missing value is in ZNS arm and if the value of  $u < p_j - \Delta$ , impute  $R_j = 1$ ; otherwise, impute  $R_j = 0$ , with  $\Delta$  varies from 0 to  $p_j$  by an increment of .05. This effectively penalizes the ZNS arm by making it less likely to have a responder.

- If the missing value is in placebo arm and if the value  $u < p_j$ , impute  $R_j = 1$ ; otherwise, impute  $R_j = 0$ .
- iii. Draw a random uniform variable,  $v$ , between 0 and 1. If  $v < 0.5$ , then impute baseline severity = 3; otherwise, impute baseline severity = 2.
- c. Analyze the data using the model as in primary analysis.
- d. Repeat the steps b-c above 25 times.
- e. Combine the results using Rubin's rule ([Rubin 1987](#)).

